	
pathology, or
 
 if the thoraco-abdomino-pelvic scans carried out at 6 and 12 months after the EUS-FNA indicate the presence of progressive neoplastic pathology. In case of doubt and if the doctor taking care of the patient deems it necessary, additional examinations may be carried out to confirm this diagnosis. 
Absence of malignancy: if the thoraco-abdomino-pelvic scans carried out 6 and 12 months after the EUS-FNA indicate the absence of progressive neoplastic pathology. In case of doubt and if the doctor taking care of the patient deems it necessary, additional examinations may be carried out to confirm this diagnosis.
 
 The technique evaluated is EUS-FNA. In particular, we consider that there is: 
 Diagnosis of malignancy: if the histology carried out on the material taken by the endoscopic puncture shows a malignant tumor. Absence of malignancy: if the histology carried out on the material taken by the endoscopic puncture shows a benign pathology (benign tumor, sarcoidosis). Atypical, suspect or non-contributory result, diagnosis of malignancy / benignity impossible. The sensitivity corresponds to the rate of subjects with a diagnosis of malignancy (without taking into account atypical / suspect or non-contributory results) according to the EUS-FNA results (index test) among all the subjects considered to be suffering from a neoplastic pathology according to the reference test. 
Secondary endpoints are:
 
 The negative predictive value of EUS-FNA will be evaluated. It corresponds to the rate of subjects with a diagnosis of benign pathology according to the reference test among all the subjects for whom EUS-FNA reveals a benign pathology (without taking into account atypical / suspect or non-contributory results). 
Impact on care will be evaluated in 2 ways based on (i) clinical utility and (ii) concordance between the MTM1/ MTM2 therapeutic strategies.
 
The clinical utility of endoscopic ultrasound puncture (Groups A and B)
 
 The puncture will be considered to have clinical utility, if it makes it possible to avoid more invasive diagnostic procedures (mediastinoscopy or thoracoscopy for patients in group A) or if it allows the patient to benefit from an appropriate treatment (result of the malignant biopsy) or to avoid receiving an unjustified treatment (result of the benign biopsy): case of patients well classified in malignant / benign by the EUS-FNA. The EUS-FNA will be considered to have no clinical utility if the result of is invalidated by the reference examination, or if the result of the puncture does not allow a diagnosis to be made. 
Agreement between MTM1 / MTM2 therapeutic strategies
 
In all patients, the agreement between the therapeutic strategies taken before and after the results of the EUS-FNA will be assessed.
 
 Therapeutic strategy for the mediastinal lymph nodes described at inclusion envisaged in MTM 1 
 Surgery from the outset Chemotherapy or other cancer treatment Non-cancer management in the event of a suspected benign pathology No treatment Therapeutic strategy for the mediastinal lymph nodes described at inclusion envisaged in MTM2 
 Surgery from the outset Chemotherapy or other cancer treatment Non-cancer management in case of benign pathology Other surgical diagnostic procedure

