Statistical analysis	
Patient characteristics at inclusion
 
The patients included will be described according to the following characteristics:
 
 • Compliance with eligibility criteria • Epidemiological characteristics 
The diagnosed mediastinal lymphadenopathy will be described:
 
 • On PET scan: injected dose, fixation time, location, size of the minor axis (mm), fixation grade (0 to 4), SUV max mediastinal vascular background, SUV max hepatic background, SUV max lymph nodes, SUV max tumor, N / T ratio, N / Liver ratio. • Endoscopic ultrasound: number of lymph nodes, location, shape, size, echogenicity, characteristics of the boundaries. • Quality of samples obtained by EUS-FNA. • Pathological characteristics: malignant tumor, benign tumor or sarcoidosis, atypical or suspect, non-contributory. 
Definitions of the study populations
 
 • Eligible population • All patients meeting the eligibility criteria. Patient eligibility will be established by the steering committee on a case-by-case basis. • Eligible and assessable population for the main criterion 
All the patients included in the study, for whom 1) the eligibility criteria are met, 2) the results of the endoscopic guided puncture are contributory.
 
Analysis of judgment criteria
 
 • The characteristics of the patients at inclusion will be described from the eligible population • The main and secondary criteria will be described on the basis of the eligible and assessable population • Subgroup analyses, in particular by type of cancer, may be

	
considered, but only on an exploratory basis.
 
• Quantitative variables will be described using descriptive statistics (range, quartile and median).• Qualitative variables will be described on the basis of the proportions and presented with their 95% confidence interval.
--	--

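### Sensitivity is computed only in patients with a contributory puncture, and the plan contradicts itself on who is counted for care impact

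*Combined protocol and SAP*

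**What the plan says.** **Sensitivity, Evaluation criteria section.** The definition reads "The sensitivity corresponds to the rate of subjects with a diagnosis of malignancy (without taking into account atypical / suspect or non-contributory results"), and its denominator is "among all the subjects considered to be suffering from a neoplastic pathology according to the reference test".

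**Analysis population, Statistical analysis section.** Under the study populations, a patient is assessable for the main criterion if eligible and if "the results of the endoscopic guided puncture are contributory". Under the analysis of the criteria: "The main and secondary criteria will be described on the basis of the eligible and assessable population".

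**Result classes.** The Evaluation criteria section puts all inconclusive results in one class: "Atypical, suspect or non-contributory result, diagnosis of malignancy / benignity impossible". The Statistical analysis section lists four classes, with two kinds of inconclusive result kept apart: "malignant tumor, benign tumor or sarcoidosis, atypical or suspect, non-contributory". Neither section says which classes are contributory.

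**Care impact, Evaluation criteria section.** A puncture has no clinical utility if the reference examination overturns it, or "if the result of the puncture does not allow a diagnosis to be made". On the treatment strategies of the two multidisciplinary meetings (MTM1 and MTM2): "In all patients, the agreement between the therapeutic strategies taken before and after the results of the EUS-FNA will be assessed". Any difference between the two strategies is scored as an impact on treatment. The option of a further surgical diagnostic step is on the MTM2 list only, and the Study procedure section ties it to a non-contributory result.

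**The concern.** Under the Statistical analysis section, a patient with cancer whose puncture is non-contributory is removed from the sensitivity denominator because of what the index test returned. Such a patient can never be in the numerator, so removal can only raise sensitivity or leave it unchanged. The objective is the performance of EUS-FNA in patients with PET-positive nodes. The headline figure would instead be performance given that the puncture worked. In a feasibility study, how often the puncture yields a diagnosis is itself a main result.

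Because contributory is undefined, two analysts could report different sensitivities from the same data, depending on whether atypical and suspect results stay in.

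For care impact, the scoring rules provide for punctures that give no diagnosis, but the stated population removes at least the non-contributory ones. Following the Statistical analysis section overstates clinical utility and the share of invasive procedures avoided. Following the Evaluation criteria section raises a different problem for MTM1/MTM2 agreement: an inconclusive puncture followed by a further surgical diagnostic step always scores as impact, because MTM1 has no matching option.

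**Working it through.** **Inputs from the documents:** 50 patients; expected sensitivity 95%; stated precision 12%, interval 89% to 100% (section on the number of inclusions). **Not in the documents:** the inconclusive rate and the share of patients who are reference-positive. All values used for these below are assumed.

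**1. The plan's own precision figure.** Wald half-width = 1.96 × √(0.95 × 0.05 / 50) = 6.04 points. The full width is 12.1 points and the interval 89.0% to 101.0%, cut at 100%. This reproduces the plan, with 12% as the full width, but only if all 50 patients are in the sensitivity denominator. Under the Statistical analysis section the denominator is patients who are both reference-positive and contributory. With an assumed 50% to 80% reference-positive and 10% to 20% of those removed:

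- 50 × 0.5 × 0.8 = 20 patients, half-width 9.6 points
- 50 × 0.8 × 0.9 = 36 patients, half-width 7.1 points

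**2. Shift in the estimate.** Let f be the share of reference-positive patients removed as inconclusive. Sensitivity in all reference-positive patients = contributory-only sensitivity × (1 − f). With 95% reported:

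| Assumed f | All reference-positive | Gap (points) |
|---|---|---|
| 5% | 0.95 × 0.95 = 90.3% | 4.7 |
| 10% | 0.95 × 0.90 = 85.5% | 9.5 |
| 20% | 0.95 × 0.80 = 76.0% | 19.0 |

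At f = 20% the gap exceeds the whole planned interval width of 12 points.

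**3. Effect of leaving contributory undefined.** Assume 30 reference-positive patients: 24 malignant on puncture, 1 benign, 2 atypical or suspect, 3 non-contributory. Exact (Clopper-Pearson) 95% intervals:

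| Removed from the denominator | Sensitivity | 95% CI |
|---|---|---|
| All five inconclusive | 24/25 = 96% | 80 to 99.9% |
| Non-contributory only | 24/27 = 89% | 71 to 98% |
| None | 24/30 = 80% | 61 to 92% |

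**4. Undetermined reference status.** A separate assumed case: 28 confirmed reference-positive (24 malignant on puncture, 1 benign, 3 inconclusive) plus 2 inconclusive with unknown reference status. Counting both as reference-negative gives 24/28 = 86% (67 to 96%). Counting both as reference-positive gives 24/30 = 80% (61 to 92%).

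**5. Clinical utility.** A separate assumed case: 5 of 50 inconclusive, 43 of the other 45 correctly classified.

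- All five removed: 43/45 = 96% (85 to 99.5%).
- Two of the five atypical or suspect and kept: 43/47 = 91%.
- All kept and scored as no utility: 43/50 = 86% (73 to 94%).

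**6. MTM1/MTM2 impact.** Same 50 patients; assume 20 of the 45 contributory patients are discordant and all five inconclusive ones are assigned a further surgical diagnostic step. This is the extreme case, since it in effect places all five in Group A, where surgical biopsy is possible.

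- Contributory only: 20/45 = 44%.
- All patients, rule as written: (20 + 5)/50 = 50%.
- All patients, inconclusive punctures not credited as impact: 20/50 = 40%.

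**7. Negative predictive value.** Its denominator is patients with a benign puncture result, so removing inconclusive results does not change it.

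**The case against.** The strongest reply is that the two sections can be made to agree on sensitivity. The parenthesis on inconclusive results also appears in the definition of negative predictive value, where it sits with the denominator and most naturally means excluded. Read the same way for sensitivity, the plan prespecifies a conditional sensitivity, which is a debatable choice but consistent. This stands in part. The wording is ambiguous, since the denominator is also said to be all reference-positive subjects, and the Statistical analysis section resolves the ambiguity towards removal. The case on sensitivity therefore does not rest on a contradiction. It rests on the denominator depending on the index test's result and on contributory being undefined.

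On clinical utility, if atypical and suspect results count as contributory, the no-diagnosis rule still operates on them and only non-contributory punctures conflict. That narrows the contradiction without removing it. On agreement, all patients could mean both Group A and Group B rather than all punctures. The MTM2 option reserved for non-contributory results counts against that reading.

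The plan scores impact without calling it favourable, so the objection to crediting inconclusive punctures concerns how the figure will be read. It is a distinct point, but it arises as soon as all patients are analysed.

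The four result classes will be described with proportions and confidence intervals, so the inconclusive rate will be visible, though not split by reference status. Finally, the all-patient figure has biases of its own (see the fix). This stands, and is why both figures should be shown.

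**Conclusion.** The concern holds. As written, the sole primary endpoint is conditional on the puncture having produced a usable result, and the direction of the effect on sensitivity (upward or none) needs no assumption. Its size cannot be fixed from the documents: every shift shown rests on assumed inconclusive rates and counts, and only the 95% and the 50 patients come from the plan. For care impact the two sections contradict each other, at least for non-contributory punctures, however contributory is read. The study is an exploratory pilot with no decision threshold, so this does not undermine the design, but it should be corrected before results are reported.

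**What to change.** 1. **Sensitivity.** Drop the requirement of a contributory puncture. Use all eligible reference-positive patients with an attempted EUS-FNA, counting atypical, suspect, non-contributory and failed punctures as not detected. Report the contributory-only sensitivity beside it, with the inconclusive proportion. State which result classes are contributory, and reword the parenthesis in the definition to match.
2. **Clinical utility and procedures avoided.** Analyse in all eligible punctured patients, as the scoring rule already implies, and correct the sentence that assigns secondary criteria to the contributory-only population.
3. **MTM1/MTM2 agreement.** Analyse in all patients, with inconclusive punctures tabulated separately, so that a further surgical diagnostic step after a failed puncture is not read as a favourable impact.
4. **Reference status of inconclusive patients.** Take it from the 12-month follow-up data already collected, report how many remain undetermined, and give bounds counting them all reference-negative and all reference-positive.

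The cost is SAP wording, one extra tabulation and one bounding analysis. Sensitivity and clinical utility will look less favourable if any punctures are inconclusive. Reference status is less certain for these patients, because scheduled 6- and 12-month scans are specified only after a negative biopsy. The reference is also per patient, so an inconclusive puncture of a benign node in a patient with cancer elsewhere could count as a missed cancer and bias the all-patient figure downward. Showing both sensitivities and the bounds lets the reader judge this.

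### The analysis section limits all secondary criteria to contributory punctures, so clinical utility loses the failures that its own definition counts; MTM agreement is probably affected too

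*Combined protocol and SAP*

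**What the plan says.** Two parts of the combined protocol and SAP bear on this.

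**Statistical analysis.** One restricted set is defined, under the title "Eligible and assessable population for the main criterion". It requires that the patient is eligible and that "the results of the endoscopic guided puncture are contributory". The section then says: "The main and secondary criteria will be described on the basis of the eligible and assessable population". The wider eligible population is assigned only to characteristics at inclusion. These include "Pathological characteristics: malignant tumor, benign tumor or sarcoidosis, atypical or suspect, non-contributory".

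**Evaluation criteria, secondary endpoints.**
- Negative predictive value: the definition itself leaves out inconclusive results.
- Clinical utility: success covers avoiding a more invasive procedure in group A, or treatment being rightly given or rightly withheld, summarised as "case of patients well classified in malignant / benign by the EUS-FNA". There is no utility if the reference contradicts the result, or "if the result of the puncture does not allow a diagnosis to be made".
- MTM agreement: "In all patients, the agreement between the therapeutic strategies taken before and after the results of the EUS-FNA will be assessed". Any discrepancy counts as an impact of the puncture.
- Side effects: to be collected in every case.

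The index-test categories in the same section include: "Atypical, suspect or non-contributory result, diagnosis of malignancy / benignity impossible".

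**The concern.** The clinical utility definition has a failure category written for punctures that yield no diagnosis. The analysis rule removes the non-contributory ones before the rate is computed. An analyst who follows the rule literally reports utility only among punctures that worked. In a feasibility study, how often the puncture fails to give an answer is a large part of the question.

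Agreement between the two MTM decisions is described for all patients, and the MTM2 list includes a further surgical diagnostic procedure. The Study procedure section links that option to a non-contributive result. The endpoint therefore seems to foresee the very patients whom the analysis rule drops. Side effects raise a milder version of the same problem: they are collected from everyone but, read literally, described only in patients with a contributory puncture.

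**Working it through.** The plan states no figure for these endpoints. Its only precision statement concerns sensitivity and does not enter here.

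**Inputs.** N = 50 is the planned size. The documents give no non-contributory count (NC), no count of results invalidated by the reference (INV) and no number of strategy changes. All of these are assumptions below.

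**Clinical utility.** Let q = NC/N.
- Analysis rule: (N − NC − INV)/(N − NC)
- Endpoint definition: (N − NC − INV)/N
- Ratio of the first to the second: N/(N − NC) = 1/(1 − q)

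The numerator is the same in both, so the ratio does not depend on INV. With INV = 2, no atypical/suspect results, and exact (Clopper-Pearson) 95% intervals:

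| NC | Analysis rule | Endpoint definition | Difference | 1/(1−q) |
|---|---|---|---|---|
| 1 | 47/49 = 95.9% [86.0; 99.5] | 47/50 = 94.0% [83.5; 98.7] | 1.9 points | 1.020 |
| 5 | 43/45 = 95.6% [84.9; 99.5] | 43/50 = 86.0% [73.3; 94.2] | 9.6 points | 1.111 |
| 10 | 38/40 = 95.0% [83.1; 99.4] | 38/50 = 76.0% [61.8; 86.9] | 19.0 points | 1.250 |

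The restricted rate stays near 95% while the rate that the definition implies falls from 94% to 76%.

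**Meaning of contributory.** The term is not defined. Assume 5 non-contributory, 3 atypical/suspect and 2 invalidated results, which leaves 50 − 5 − 3 − 2 = 40 successes:
- atypical/suspect treated as not contributory: 40/42 = 95.2%
- atypical/suspect treated as contributory, and so counted as failures: 40/45 = 88.9%
- all patients: 40/50 = 80.0%

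**MTM agreement.** Assume 27 strategy changes among 45 contributory patients, with d further changes among the 5 non-contributory ones.
- Analysis rule: 27/45 = 60.0%
- All patients: (27 + d)/50, from 27/50 = 54.0% (d = 0) to 32/50 = 64.0% (d = 5)

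The two agree only at d = 3 (30/50 = 60.0%), so the restricted figure can be too high or too low. A further surgical diagnostic procedure is in the MTM2 list but not the MTM1 list, so choosing it always counts as a change.

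**The case against.** The best defence is that little information is lost. The non-contributory category is to be described among characteristics in the eligible population. Since every such result is a utility failure, a reader can rebuild 43/50 from 43/45 plus the reported 5. The endpoints are descriptive, no decision rule depends on them, and the label of the set suggests a drafting slip. This holds as mitigation and limits the severity. It does not remove the contradiction: the reported percentage and its planned confidence interval would still use the wrong denominator. Nor does it help with MTM agreement, where the count alone does not recover the all-patient figure.

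On MTM agreement, the phrase covering all patients follows a clinical utility heading that names groups A and B. It may mean only that both groups are included. That is a fair reading and makes this conflict probable, not certain. The MTM2 option linked to non-contributive results weighs the other way.

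A reader might infer three stronger points, which the documents do not support:
- That the no-diagnosis criterion for utility can never apply. This is true only if atypical/suspect results are not contributory. Both sections name them separately from non-contributory results, so the more natural reading keeps them in the set, where the criterion still applies to them.
- That procedures avoided is a separate endpoint with no rule for a failed puncture. The utility definition already contains it and scores a puncture without a diagnosis as no utility.
- That every secondary result is biased upward. Negative predictive value is consistent with the restricted set, and MTM agreement can move either way.

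**Conclusion.** The concern holds for clinical utility, with high confidence. Two current sections give different denominators, nothing in the document says which governs, and following the analysis section can only raise the rate or leave it unchanged. The factor 1/(1−q) is exact algebra, given that non-contributory punctures score as no utility. The differences of 1.9, 9.6 and 19.0 points rest on assumed counts and are illustrations, not predictions.

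For MTM1/MTM2 agreement the conflict is probable, confidence is moderate and the direction of bias is unknown. For side effects there is a tension between who is observed and who is described. The undefined term contributory is an ambiguity to settle, not a second contradiction.

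This should be fixed. It is not more serious than that, because the endpoints are secondary and descriptive in an exploratory pilot and the non-contributory count will be visible.

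**What to change.** Replace the single sentence on populations with one population per endpoint:
- **Negative predictive value and other accuracy measures whose definitions exclude inconclusive results:** keep the assessable set.
- **Clinical utility, including its procedures-avoided component in group A:** all eligible patients who underwent EUS-FNA, with non-contributory and atypical/suspect results counted as no utility, as the endpoint definition implies.
- **MTM1/MTM2 agreement:** all eligible patients with both strategies recorded, with non-diagnostic punctures shown separately.
- **Side effects:** all punctured patients.
- **Definition:** state whether atypical/suspect results are contributory.

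The cost for clinical utility is a less favourable reported figure wherever non-contributory results occur. For MTM agreement, new wording may not be enough. The Study procedure text places the MTM1 therapeutic strategy under group B. The Study design flowchart, which text conversion may have distorted, places it on the branch where surgery is possible. The agreement endpoint expects it in all patients. The sponsor must reconcile these places and confirm that the strategy is recorded in both groups before agreement can be computed in all patients.

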--	--

	
 ○ No treatment • Agreement between the 2 strategies considered: for any discrepancy between the 2 strategies considered before the endoscopic puncture and after, the puncture will be considered to have had an impact on the treatment. • Side effects In all cases, the side effects associated with performing the EUS-FNA will be collected and classified according to the Clavien-Dindo classification of surgical complications [Clavien P et al. Ann Surg 2009; 250: 187-96].
Number inclusions necessary of	
This project is an exploratory pilot study, the main objective of which is to evaluate the performance of EUS-FNA via the esophagus, carried out after a PET scan showing hypermetabolic lymphadenopathy. Again, the main judgment criterion is sensitivity.
 
Due to the small amount of data available in the literature concerning the sensitivity and specificity of this examination, we did not calculate a number of patients necessary, but determined the number of patients taking into account the feasibility and recruitment criteria possible at Institut Bergonié as well as acceptable precision of the estimations.
 
For 50 patients, we estimated that the precision of the sensitivity and specificity estimate would be 12% for an expected sensitivity of 95% (95% confidence interval: [89%; 100%]) [Kalade AV et al. Intern Med J. 2008 - sensitivity and specificity of EUS-FNA coupled with PET Scan, but for histology data, whereas in our project we will have cytology data].

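### Side effects have no analysis population covering every punctured patient: the stated rule limits secondary criteria to eligible patients with a contributory sample

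*Combined protocol and SAP*

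**What the plan says.** In the Evaluation criteria section, a list opens with "Secondary endpoints are" and runs through negative predictive value, impact on care and side effects. On the last of these it says: "In all cases, the side effects associated with performing the EUS-FNA will be collected and classified", using the Clavien-Dindo system. The same section foresees punctures that give no diagnosis: "Atypical, suspect or non-contributory result, diagnosis of malignancy / benignity impossible".

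The Statistical analysis section defines two populations.

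- **Eligible population.** Patients who meet the eligibility criteria, with this condition: "Patient eligibility will be established by the steering committee on a case-by-case basis". Its one stated use is: "The characteristics of the patients at inclusion will be described from the eligible population".
- **Restricted population.** This is headed "Eligible and assessable population for the main criterion". It requires that eligibility is met and that "the results of the endoscopic guided puncture are contributory".

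Under Analysis of judgment criteria, the restricted population is then applied to all endpoints: "The main and secondary criteria will be described on the basis of the eligible and assessable population". The section does not mention side effects and names no safety population.

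**The concern.** A patient is exposed to the risks of EUS-FNA (general anesthesia and three needle passages per node, according to Study procedure) whatever the sample later shows and whatever the steering committee decides about eligibility. Limiting the complication rate to contributory punctures conditions it on a result of the procedure itself. The rate then describes a subset chosen after exposure.

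The direction of any error depends on where the events fall. The rate is too low if complications are more frequent in the excluded patients, and too high if they are more frequent in those with a contributory sample. If the two are unrelated, there is no expected bias, but collected events can still go unreported and precision falls. The documents do not say which case applies. In a feasibility study of 50 patients, one or two events make up much of the safety evidence.

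**Working it through.** **Reading the text**

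1. *If side effects are a secondary criterion*, as their place in the list suggests, the general rule puts them in the restricted population. Punctured patients with a non-contributory result, or ruled ineligible, are left out.
2. *If they are not*, because the secondary objectives in the Summary do not mention them, the statistical section gives them no population at all. The eligible population does not fill the gap: it is assigned to characteristics at inclusion and also omits patients ruled ineligible.

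On neither reading does a denominator cover everyone who had the procedure.

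**Illustrating the size**

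The plan has no figure of its own to reproduce here. Inputs:

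- From the plan: N = 50.
- Assumed: 3 complications among the 50 patients.
- Assumed: 10%, 20% or 30% non-contributory, so 5, 10 or 15 patients excluded and denominators of 45, 40 or 35. Patients ruled ineligible would lower these further.

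Intervals are exact (Clopper-Pearson) 95%. The rate in all exposed patients is 3/50 = 6.0% (1.25% to 16.55%).

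The restricted rate depends on how many of the 3 events fall in contributory patients:

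| Events counted | n = 45 | n = 40 | n = 35 |
|---|---|---|---|
| 0 | 0% (upper limit 7.87%) | 0% (upper limit 8.81%) | 0% (upper limit 10.0%) |
| 1 | 2.2% (0.06–11.77) | 2.5% (0.06–13.16) | 2.9% (0.07–14.92) |
| 2 | 4.4% (0.54–15.15) | 5.0% (0.61–16.92) | 5.7% (0.70–19.16) |
| 3 | 6.7% (1.40–18.27) | 7.5% (1.57–20.39) | 8.6% (1.80–23.06) |

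With three events, the restricted rate exceeds 6.0% only if all three fall in contributory patients. If even one falls outside, the rate is understated.

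**If events are unrelated to the sample result**

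- Expected events left out: 3 × 5/50 = 0.3; 3 × 10/50 = 0.6; 3 × 15/50 = 0.9.
- Expected restricted rate: 2.7/45 = 2.4/40 = 2.1/35 = 6.0%, so no bias on average.
- Chance that at least one event is left out, with e patients excluded and k events: 1 − C(50−e, k)/C(50, k). For k = 3, C(50,3) = 19,600:
  - e = 5: 1 − 14,190/19,600 = 0.276
  - e = 10: 1 − 9,880/19,600 = 0.496
  - e = 15: 1 − 6,545/19,600 = 0.666

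Because the event count is assumed, the same formula for other values of k gives:

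| Events in 50 | 5 excluded | 10 excluded | 15 excluded |
|---|---|---|---|
| 1 | 10% | 20% | 30% |
| 2 | 19% | 36% | 51% |
| 3 | 28% | 50% | 67% |

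It is also unclear whether atypical or suspect results count as contributory. If they do not, more patients are excluded.

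**The case against.** The best counter-argument is that the side-effects item sets its own scope by covering every case, and a specific statement should prevail over a general one. Classifying every event by grade is already much of a descriptive safety analysis in a single-arm study. The general rule also looks loosely drafted. The restricted population is headed as serving the main criterion. Agreement between the two multidisciplinary meetings is to be assessed in all patients. A puncture that gives no diagnosis counts as lacking clinical utility, which presupposes that such patients are analyzed. Excluding side effects was therefore probably not intended.

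Much of this is fair as a reading of intent, but it does not settle the matter. The side-effects item governs collection and grading. The only text that assigns analysis populations is the statistical section, and it extends the restricted set to the secondary criteria without exception. Evidence of loose drafting there is a reason to correct it.

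Four further points stand as limits:

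- The document is a translated study summary, and its lists may have lost their original nesting, so the finding applies to the text as available.
- The plan does not say when eligibility is ruled on, so exclusion for ineligibility after puncture is possible but not stated.
- The illustration rests wholly on assumed rates.
- Because the data will exist for everyone, an omission can be recovered at reporting. That limits the harm, but a pre-specified rule should not depend on it.

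**Conclusion.** The concern holds. Following the written rule leaves complications in some punctured patients out of the described rate; on the alternative reading, side effects have no stated analysis population. The size cannot be fixed from the documents. Under the assumed 3 events in 50 and 10% to 30% non-contributory results, a true observed rate of 6.0% could be reported as anything from 0% to 8.6%. With no association between events and sample result there is no expected bias, but there is a 28% to 67% chance that at least one event goes undescribed (10% to 30% if only one event occurs). The intervals overlap widely at these sizes, so no particular distortion is demonstrated. The fault is a wrong denominator in the stated rule. It should be corrected; it does not affect the sensitivity analysis.

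**What to change.** Under Analysis of judgment criteria, exempt side effects from the restriction to the eligible and assessable population and add a sentence such as:

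> *Side effects are described by Clavien-Dindo grade, with proportions and 95% confidence intervals, in all patients in whom EUS-FNA was performed or attempted, whatever the eligibility ruling or the sample result.*

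The section already requires 95% confidence intervals for proportions, so this adds no new method. The cost is one sentence. No new data are needed, because side effects are already collected and graded for everyone, and clinical management is unchanged.
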